9.4 Analysis Populations

9.4.1 Modified Intent-to-Treat (mITT) Population

The mITT population will include all randomized subjects who have received at least one dose of study medication. This population will be the primary population for efficacy analyses and will be used to summarize a subset of efficacy variables and will summarize subjects as randomized.

9.4.2 Per Protocol (PP) Population

The PP population is a subset of the mITT population, which will include those subjects (and their visits) who do not have major protocol deviations likely to seriously affect the primary outcome of the study. This population will be the secondary population for efficacy analyses and will be used to summarize a subset of efficacy variables. If the PP and mITT populations are exactly the same, then additional efficacy analyses on the PP population will not be performed. The PP population will summarize subjects as treated.

9.4.3 Safety Population

The safety population will include all randomized subjects who have received at least one dose of investigational product. This population will be used to summarize safety variables and will summarize subjects as treated.

9.5 Demographics and Baseline Characteristics

Demographic and baseline characteristics such as age, gender, race, and ethnicity will be summarized and listed. Medical history, history of ocular surgery and procedures will also be summarized and listed.

9.6 Subject Disposition

Subject disposition will be presented in terms of the numbers and percentages of subjects who completed the study and discontinued from the study. Disposition will be summarized by treatment group and for all subjects.

The number of randomized subjects in each of the analysis populations (mITT, PP, and Safety) will be displayed by treatment.

The number and percentage of subjects who prematurely discontinue from the study and the reasons for study discontinuation will be summarized by treatment group for all subjects.

9.7 Primary Endpoint(s)

9.8 Efficacy Analysis

9.8.1 Primary Efficacy Endpoint

The primary efficacy endpoint is the mean change from baseline in mean CCT as assessed by ultrasound pachymetry at Week 4.

9.8.2 Primary Efficacy Analyses

The primary comparisons in this trial will be within a treatment group on the mean change from baseline CCT to Week 4/Day 28 (Visit 4) for each of netarsudil QD and BID.

The primary efficacy endpoint change from baseline CCT will be summarized descriptively (n, mean, standard deviation, median, min, and max) and analyzed primarily using one-sample t-tests; comparisons between treatment groups will be completed using two-sample t-tests. Sensitivity analyses will be completed using Wilcoxon signed-rank tests within a treatment group, Wilcoxon rank sum tests between treatment groups and an ANCOVA model with terms for baseline CCT value, treatment. The least squares mean will be presented for each treatment group from the model together with two-sided p-values and 90 and 95% confidence intervals around the change from baseline within each treatment group. Comparisons between treatment groups on the change from baseline CCT will also be made including the least squares mean difference and corresponding two-sided p-values and 90 and 95% confidence intervals.

The primary analysis will use the mITT population with available data per subject. Robustness analyses will also be presented based on the multiple imputation methodology under different assumptions of missingness and intercurrent events (at random and not at random), using last observation carried forward (LOCF), and using the per protocol population with available data per subject.

Intercurrent events will be primarily handled in the following manner:

1. Discontinuation of study medication and non-optimal compliance will be ignored, values measured after discontinuation of study medication or regardless of compliance will be used in the analyses [treatment policy strategy].
2. Withdrawal due to lack of efficacy or adverse events: missing data will be singly imputed as the worst within subject observation prior to the intercurrent event [hypothetical strategy].
3. Missing data without withdrawal or withdrawal due to reasons other than lack of efficacy or adverse events: missing data will be imputed employing Multiple Imputation (MI) using randomized treatment-based Markov Chain Monte Carlo (MCMC) methodology to impute non-monotone missing data and regression methodology to impute monotone missing data [hypothetical strategy].

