3.2 Rationale for Study Design and Control Group

Current treatment options for FCD include hyperosmotic saline ophthalmic drops/ointments and surgical procedures. Hyperosmotic saline can provide temporary symptomatic relief by facilitating corneal dehydration. Endothelial keratoplasty using donor corneas is currently the gold standard therapeutic option to restore vision in patients with FCD. Although improvement of surgical techniques has enabled less invasive treatment and better outcomes, corneal transplants require long-term steroid use and are still associated with difficult surgical techniques, graft rejection, acute/chronic cell loss, and worldwide donor cornea shortages ([Okumura 2017](#)). A relatively new non-transplant surgical procedure known as Descemet Stripping Only (DSO) or Descemetorhexis Without Endothelial Keratoplasty (DWEK) is also now available for a minority of FCD patients.

A pharmacologic alternative to surgery in patients with FCD would be very beneficial, even if pharmacologic treatment only delays the need for surgery.

This study is designed to investigate the efficacy and safety of netarsudil for the treatment of FCD and to enable optimal study design for further clinical development. The optimal dosing regimen will provide maximum reduction in corneal edema due to FCD with minimal adverse effects.

It should be noted that, since FCD is a slowly progressing disease, surgery is rarely urgent, and patients are often seen multiple times before undergoing surgery. Therefore, an approximate 8 to 9-week delay in surgery for participation in this study is acceptable.

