9. PLANNED STATISTICAL METHODS

9.1 General Considerations

Continuous study assessments will be summarized by treatment and time point (as applicable) using descriptive statistics (n, mean, median, standard deviation, minimum, and maximum). Categorical study assessments will be summarized by treatment and visit (as applicable) using frequency counts and percentages. Hypothesis testing, unless otherwise indicated, will be performed at a 2-sided 0.10 significance level. Where applicable, 2-sided 90% and 95% CIs will be reported. All p-values will be displayed to four decimal places, with p-values less than 0.0001 presented as '<0.0001' and p-values greater than 0.9999 presented as '>0.9999'. Difference between netarsudil QD and netarsudil BID will be calculated as netarsudil QD – netarsudil BID.

All study data will be listed by treatment, subject and time point (as applicable).

Statistical methods will be more fully described in a separate Statistical Analysis Plan.

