## 12.2 Primary Efficacy Analysis

The primary comparisons in this trial will be within a treatment group on the mean change from baseline CCT by ultrasound pachymetry at Week 4/Day 28 (visit 4) for each of netarsudil QD and BID. The summary will be provided for the study eye. The primary efficacy endpoint change from baseline in CCT will be summarized using continuous descriptive statistics and analyzed primarily using one-sample t-tests by treatment group; comparisons between treatment groups (QD – BID) will be completed using two-sample t-tests. Sensitivity analyses will be completed using Wilcoxon signed-rank tests within a treatment group, Wilcoxon rank sum tests between treatment groups and an analysis of covariance (ANCOVA) model with terms for baseline CCT value and treatment.

The mean change from baseline in CCT for each treatment group along with 2-sided p-values and 90% and 95% CIs around the change from baseline within each treatment group for the mean from one-sample t-test will be presented. The mean difference in change from baseline between treatment groups along with 2-sided p-values and 90% and 95% CIs for the mean differences between treatment groups from two-sample t-test will be presented. P-values from Wilcoxon signed-rank test within each treatment group, and Wilcoxon rank-sum test between treatment groups will be presented. The least squares (LS) mean for each treatment group along with 2-sided p-values and 2-sided 90% and 95% CIs around the change from baseline within each treatment group will be presented from the ANCOVA model.

Comparisons between treatment groups on the change from baseline in CCT will also be made including the LS mean difference and the corresponding 2-sided p-values and 90% and 95% CIs.

Example SAS® code for the primary efficacy analysis on change from baseline (CHG\_CCT):

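### The QD–BID comparison of continuous endpoints is led by an unadjusted t-test, with the planned baseline-adjusted ANCOVA only a sensitivity analysis (minor)

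*Protocol*

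**What the plan says.** Protocol 9.8.2 sets the order for CCT at Week 4. The main question is asked within each regimen: "The primary comparisons in this trial will be within a treatment group on the mean change from baseline CCT", tested by one-sample t-tests. For QD against BID it says "comparisons between treatment groups will be completed using two-sample t-tests". The sensitivity analyses then include "Wilcoxon rank sum tests between treatment groups and an ANCOVA model with terms for baseline CCT value, treatment". The synopsis has the same order. SAP 12.2 repeats it: "comparisons between treatment groups (QD – BID) will be completed using two-sample t-tests", with "an analysis of covariance (ANCOVA) model with terms for baseline CCT value and treatment" again listed as a sensitivity analysis.

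The adjusted contrast is nevertheless fully specified. Protocol 9.8.2 has the between-regimen comparison reported "including the least squares mean difference and corresponding two-sided p-values and 90 and 95% confidence intervals". SAP 12.2 says the same and supplies ANCOVA code for observed and for imputed data.

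Protocol 9.8.4 and SAP 12.3 apply the same strategy to change in BCVA at Weeks 4 and 8 and to CCT at Week 8. For the binary endpoints (a gain of 15 letters or more, and resolution of corneal edema), those sections lead with logistic regression on treatment and the baseline measure. The unadjusted chi-squared or Fisher test is the sensitivity analysis.

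**The concern.** QD against BID is the only randomised comparison in the trial; the within-arm tests have no concurrent control. Protocol 3.2 gives the contrast a purpose when it says "The optimal dosing regimen will provide maximum reduction in corneal edema due to FCD with minimal adverse effects". In a study meant to inform later design, the quality of that estimate matters even without a formal decision attached.

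Baseline CCT is measured on everyone. It is expected to be related to change, because entry requires a high value and some regression to the mean is plausible. Protocol 5.4 and SAP 4.2 name no stratification factor, so baseline CCT can be unbalanced by chance with 20 per arm. ANCOVA corrects for that imbalance and usually narrows the interval.

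The order is also inconsistent within the plan. The same BCVA data are compared adjusted-first as a 15-letter gain and unadjusted-first as a mean change. If the adjusted and unadjusted differences disagree, the plan makes the unadjusted one the lead result. In an open-label study that ranking should be chosen deliberately and fixed before database lock.

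**Working it through.** **Inputs.** SD of change 60 µm and up to 20 per group (Protocol 9.3, SAP 5); 1:1 allocation (Protocol 5.2). Testing "will be performed at a 2-sided 0.10 significance level" (Protocol 9.1). Dropout is not stated, so 20 evaluable per group is assumed. The correlation r between baseline CCT and change is not stated; a range is used.

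**The plan's own figures.** These concern the within-arm test.
- Power: one-sample noncentral t, df 19, noncentrality 0.577 × √20, two-sided 0.10, gives 80.0% (stated 80%).
- 90% CI half-width: 1.645/√20 = 0.368, so SD/2.72 = 22.1 µm (stated SD/2.7 = 22.2 µm). This is the normal quantile; with t on 19 df it is 23.2 µm.

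Both documents are silent on power or precision between regimens.

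**Two-sample t-test.** Half-width = t(0.95, 38) × 60 × √(2/20) = 1.686 × 18.97 = 32.0 µm.

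**ANCOVA.** Expected half-width = t(0.95, 37) × 18.97 × √[(1 − r²) × 37/36]. The factor 37/36 is the average cost of chance baseline imbalance with 40 subjects. The last column is the true difference detectable with 80% power at two-sided 0.10.

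| Analysis | 90% half-width (µm) | Against t-test | Detectable difference (µm) |
|---|---|---|---|
| t-test | 32.0 | – | 48.0 |
| ANCOVA, r = 0 | 32.4 | 1.4% wider | 48.7 |
| ANCOVA, \|r\| = 0.2 | 31.8 | 0.6% narrower | 47.7 |
| ANCOVA, \|r\| = 0.3 | 31.0 | 3.2% narrower | 46.5 |
| ANCOVA, \|r\| = 0.5 | 28.1 | 12.1% narrower | 42.2 |

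The two half-widths are equal at |r| of about 0.17. A simulation of 4,000 trials per value gave ANCOVA-to-t half-width ratios of 1.014, 0.994, 0.967 and 0.877 at |r| = 0, 0.2, 0.3 and 0.5, in agreement with the table.

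**Which r is plausible?** Two illustrations with assumed CCT SDs:
- Equal SDs at baseline and Week 4: r = −60/(2 × SD). An SD of 60 to 100 µm gives |r| of 0.5 to 0.3, so a gain of 12% to 3%.
- SD 40 µm at baseline (narrowed by the 600 µm entry floor) and 70 µm at Week 4: covariance = (40² + 70² − 60²)/2 = 1450. Then r = (1450 − 40²)/(40 × 60) = −0.06, and there is no gain.

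**Chance imbalance.** A baseline imbalance of one standard error of the difference in means shifts the expected change-score difference by |r| × 60 × √(2/20) = |r| × 18.97. That is 5.7 µm at |r| = 0.3 and 9.5 µm at 0.5. ANCOVA removes this shift. Averaged over randomisations the t-test is unbiased; the shift applies to the trial in which the imbalance occurs.

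**The case against.** The strongest reply is that nothing is lost. The ANCOVA difference, its p-value and its intervals are pre-specified and will sit beside the t-test. That stands: the precision is demoted, not discarded, and a reader who infers that it is given up goes further than the documents allow.

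The contrast is also not the trial's main result. All the stated hypotheses are within-arm against zero, Protocol 9.3 says the study is not powered for a pre-stated signal, and no decision rule hangs on QD against BID. Protocol 3.2 describes what the best regimen would achieve; it does not say that one will be chosen on this test. That stands too, and it limits severity.

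A reader might take it as settled that baseline CCT predicts change, or apply the textbook variance ratio (1 + ρ)/2, where ρ is the correlation between baseline and follow-up CCT, and promise a 25% variance reduction at ρ = 0.5. The documents support neither. They give no correlation, and the ratio assumes equal variances, which the 600 µm floor at Screening and Baseline makes doubtful. It also leaves out the cost of chance imbalance. Power quoted for a 34.6 µm regimen difference would borrow the within-arm example; the plan sets no between-regimen target.

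Finally, the change-score t-test is valid under randomisation, already subtracts baseline, and gives a regimen difference equal to the difference of the two primary within-arm means. The adjusted difference need not. SAP 2.1 makes the within-arm comparison primary for means and the between-arm comparison primary for proportions, which explains some difference in emphasis. It does not explain why adjustment leads for one type of endpoint and follows for the other.

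**Conclusion.** The point holds as a minor matter of ordering. Both documents lead the non-primary, unpowered QD–BID comparison of continuous endpoints with an unadjusted t-test. They rank the planned ANCOVA below it, against their own practice for binary endpoints and without a stated reason.

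With change SD 60 µm and 20 evaluable per arm, leading with ANCOVA changes the 90% CI half-width from 32.0 µm to between 32.4 µm (r = 0) and 28.1 µm (|r| = 0.5): from 1.4% wider to 12% narrower. The range is lopsided in favour of adjustment, but where the trial falls in it depends on an r that the documents do not give. Protection against chance baseline imbalance likewise matters only so far as r differs from zero. The within-arm primary analysis and the stated sample-size figures are unaffected.

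**What to change.** In Protocol 9.8.2, the matching synopsis text and SAP 12.2, name the ANCOVA least squares mean difference (QD − BID, baseline CCT as covariate) as the lead between-regimen result and the two-sample t-test as its sensitivity analysis. Say in Protocol 9.8.4 and SAP 12.3 that the same order applies to change in BCVA, with baseline BCVA as covariate, and to change in CCT at Week 8. Leave the one-sample t-tests primary within each arm.

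The cost is wording. The model, its code and the reported quantities are already planned, and no subjects, visits or data are added. SAP 1 says its methods supersede those in the protocol, so if no protocol amendment is otherwise due, the change could be made in the SAP and recorded in SAP 15. The statistical price is one degree of freedom, and an adjusted difference that may not equal the difference of the two raw within-arm means; a table footnote can say so. Settle the order before database lock.

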9.8.3 Secondary Efficacy Endpoints

Secondary endpoints include:

- Mean change from baseline in BCVA at Week 4
- Mean change from baseline in CCT as assessed by ultrasound pachymetry at Week 8
- Mean change from baseline in BCVA at Week 8
- Proportion of subjects who gained ≥ 15 letters (3 lines) in BCVA at Week 4
- Proportion of subjects who gained ≥ 15 letters (3 lines) in BCVA at Week 8
- Proportion of subjects with complete resolution of corneal edema at Week 4
- Proportion of subjects with complete resolution of corneal edema at Week 8

9.8.4 Secondary Efficacy Analyses

The secondary efficacy analyses will be conducted in the mITT population with available data per subject. Descriptive statistics will be presented by treatment group. Summarization and analysis of the mean change from baseline in BCVA at Weeks 4 and 8 and mean change from baseline in CCT by ultrasound pachymetry at Week 8 will be completed using a similar strategy as for the primary endpoints.

Testing of the proportion of subjects who gained ≥ 15 (3 lines) in BCVA at Weeks 4 and 8 (separately) and the proportion of subjects with complete resolution of corneal edema at Weeks 4 and 8 (separately) will be completed using logistic regression with fixed effects of treatment and corresponding baseline measure.

The adjusted odds ratios and marginal proportions and difference in proportions along with corresponding two-sided 95% Confidence Intervals (CIs) and p-values will be presented.

Treatment comparisons will also be made using Pearson's chi-squared test or Fisher's exact test if any of the cell counts are less than five as a sensitivity analysis.

The primary analyses of the secondary endpoints will use the mITT population with available data per subject. Robustness analyses may also be presented based on the multiple imputation methodology under different assumptions of missingness and intercurrent events (at random and not at random), using last observation carried forward (LOCF), and using the per protocol population with available data per subject.

9.8.5 Exploratory Efficacy Endpoints

Exploratory endpoints include:

- Proportion of subjects who gained ≥ 15 letters (3 lines) in BCVA at Week 2
- Proportion of subjects who gained ≥ 10 letters (2 lines) in BCVA at Weeks 2, 4, and 8
- Proportion of subjects who gained ≥ 5 letters (1 line) in BCVA at Weeks 2, 4, and 8
- Mean change from baseline in CCT as assessed by Pentacam® at Week 4 (selected sites only)
- Mean change from baseline in V-FUCHS glare factor score at Week 4

9.8.6 Exploratory Efficacy Analyses

Exploratory endpoints will be analyzed in a similar manner as the secondary endpoints.

9.8.7 Primary Safety Assessments and Analyses

Adverse events (AEs) will be coded using the MedDRA dictionary. Frequencies and percentages of treatment-emergent adverse events (TEAEs) will be summarized at the subject level by system organ class and preferred term for all TEAEs, treatment related TEAEs, serious TEAEs, and TEAEs causing premature treatment discontinuation by treatment group. An AE is treatment emergent if it occurs or worsens after the first dose of study medication. Similar summaries will be presented for all TEAEs by maximal severity. Separate summaries will be performed for ocular and non-ocular AEs.

Best corrected visual acuity and intraocular pressure data for both the study eye and the fellow eye will be summarized for each measured visit and for change from baseline to each post-treatment visit using the continuous summary statistics.

Anterior segment biomicroscopy and ophthalmoscopy measures will be summarized at each measured visit using discrete summary statistics. Additionally for anterior segment biomicroscopy, discrete summaries will be provided by region, finding, visit, time point, and eye (study eye and fellow eye) for the number of subjects with at least one severity grade increase from baseline and for the number of subjects judged to be clinically significant by the Investigator. Shift tables from baseline may also be summarized.

Vital signs will be summarized at each measured visit and for change from baseline to each measured visit using continuous summary statistics by treatment group and visit.

10.2 Institutional Review Board (IRB) or Independent Ethics Committee (IEC) Approval

This protocol, materials used to recruit subjects, and materials used to document consent must be approved by the IRB/IEC prior to initiation of the study. The name and address of each reviewing IRB/ IEC will be documented in the Trial Master File. Written IRB/IEC approval must adequately identify the protocol and informed consent. In addition to approving the protocol, the IRB/IEC must also approve the Subject Information and Consent Form, as well as any advertising tools that will be used for the study. Written approval also must indicate whether approval was granted based on full committee review or expedited review. Copies of all approved materials, all correspondence with the IRB/IEC and written approval from the IRB/IEC must be made available to the Sponsor, prior to the start of subject enrollment into the study. The Investigator will report promptly to the IRB/IEC any new information that may adversely affect the safety of the subjects or the conduct of the study. The Investigator will submit written summaries of the study to the IRB/IEC as required. On completion of the study the IRB/IEC will be notified that the study has ended.

10.3 Ethical Conduct of the Study

The study will be conducted according to this clinical protocol and will be governed by the following directives and guidelines:

- US CFR, Title 21
- ICH – Consolidated Good Clinical Practices Guideline (E6)
- Standard Operating Procedures (SOPs) of the Sponsor and any vendors participating in the conduct of the study
- The ethical principles that have their origin in the Declaration of Helsinki

10.4 Subject Information and Consent

Written informed consent will be obtained from each subject before any subject specific procedures are initiated. A copy of the signed and dated consent document will be given to each subject. The original signed and dated informed consent document must be maintained in the study files at the Investigator's site.

The Investigator is responsible for ensuring that no subject is subject to any study-related examination or activity before that subject has given informed consent. The subject must give written consent after the receipt of detailed information. The verbal explanation will cover all the elements specified in the written information provided for the subject.

It should be emphasized that the subject is at liberty to withdraw consent to participate at any time, without penalty or loss of benefits to which the subject is otherwise entitled.

Subjects who refuse to give, or withdraw, written informed consent may not be included or continued in this study, but this will not impact on their subsequent care.

The Investigator will inform the subject of the aims, methods, anticipated benefits and potential hazards of the study, including any discomfort it may entail. The subject must be given every opportunity to clarify any points he/she does not understand and if necessary, ask for more information. At the end of the interview, the subject may be given time to reflect if this is required, or if the subject requests more time. Subjects and/or legal guardian will be required to sign and date the informed consent form.

Signed informed consent must be attained prior to the conductance of any study procedures.

